COH Amendment 04 (Title page change only)	Version 04
COH Amendment 05 (Title page change only)	Version 05
COH Amendment 06 (Title page changes dated 09/24/12)	Version 06
COH Amendment 07 (Title page change – remove [name])	Version 07
COH Amendment 08 (Title page dated 03/07/13)	Version 08
COH Amendment 09 (Protocol dated 06/11/13)	Version 09
COH Amendment 10 (Protocol dated 09/26/13 – (DSM Update)	Version 10
COH Amendment 11 (Protocol dated 11/22/13)	Version 11
COH Amendment 12 (Protocol dated 02/07/14)	Version 12
COH Amendment 13 (Protocol dated 07/07/14)	Version 13
COH Amendment 14 (Title page change only)	Version 14
COH Amendment 15 (Protocol dated 04/01/15)	Version 15

Investigator & Study Center:

[name]
City of Hope National Medical Center
[name],
[name]
[contact], [name]

*Brentuximab vedotin is the exclusive trademark of Seattle Genetics, Inc., registered in the United States and internationally.

Additional Investigator and Study Center

[name].
Weill Medical College, Cornell University
[name]
[name]
[contact]

Study Sponsor, Monitor and Data Coordinating Center: City of Hope

PROTOCOL SUMMARY

Title: A phase II study of brentuximab vedotin as salvage therapy for Hodgkin lymphoma prior to autologous hematopoietic cell transplantation (AHCT).

Objectives

The primary objective of this study is to determine the anti-tumor activity as assessed by response rate.

The secondary objectives of this study are:

- To characterize stem cell mobilization and collection post brentuximab vedotin salvage therapy.
- To characterize the toxicity profile post brentuximab vedotin salvage therapy.
- Evaluate the biological markers of Hodgkin lymphoma patients treated with brentuximab vedotin as 1st line salvage therapy.
- To examine and characterize the outcomes of patients who receive brentuximab vedotin as 1st line salvage followed by AHCT (e.g., 2-year PFS/OS/relapse-progression incidence and NRM).

Objectives of the New Cohort

As part of a new cohort, up to 20 additional patients will be accrued to the phase II study. Those patients who do not achieve CR at the end of cycle 2 will receive a dose of 2.4 mg/kg of brentuximab vedotin during cycles 3 and 4. In addition to the objectives of the Phase II study, patients treated at the higher dose will be evaluated for the impact of the higher dose on response rate and toxicity after cycle 4.

Refer to specific inclusion and exclusion criteria detailed in protocol.

Number of patients

37 (Phase II Study)

Up to 20 (New Cohort)

Study design and methodology

Phase II, (efficacy) clinical trial

Treatments administered

For the primary study objective, brentuximab vedotin will be administered at a dose of 1.8 mg/kg on day 1, every 21 days for a total of 4 cycles prior to AHCT.

In the new cohort we will treat up to 20 additional patients at the 1.8 mg/kg dose of brentuximab vedotin on day 1, every 21 days for a total of 2 cycles and then evaluate their CR response rate. Patients who achieve a CR will continue getting 1.8 mg/kg for 2 more cycles. Patients who do not achieve a CR (e.g., PR or SD) after 2 cycles of treatment, will be treated at a dose of 2.4 mg/kg on day 1, every 21 days for 2 more cycles instead of 1.8 mg/kg.

Efficacy data collected

The following evaluations will be conducted to assess the efficacy of brentuximab vedotin

- CT/PET or CT of neck, chest, abdomen, and pelvis will be performed after every 2 cycles

of brentuximab vedotin prior to AHCT

- CT/PET scan to be performed at the end of 4 cycles but prior to AHCT.
- CT/PET and CT of the neck, chest, abdomen, and pelvis to be performed at baseline.
- Bone marrow biopsy will be performed at baseline. If positive at baseline, it will be performed after 4 cycles of brentuximab vedotin. If bone marrow biopsy was negative at baseline, it will not need to be repeated.
- Correlative studies of treatment effects on Hodgkin lymphoma biomarkers.
- Diagnostic lymph node samples will be examined for CD 68 expression and intensity.
- Repeat lymph node biopsy will be performed on patients who failed to achieve a partial remission if patient has an accessible node.

Safety data collected

- Specific safety measurements are detailed in section 3.6.3 and section 4.

Statistical procedures

Specific statistical procedures are detailed in section 5.

TABLE OF CONTENTS

PROTOCOL SUMMARY	3
TABLE OF CONTENTS	5
1 INTRODUCTION.....	11
1.1 Background on Relapsed or Refractory Hodgkin Lymphoma.....	11
Table 1 Single-agent Phase 2 Studies in Relapsed/Refractory HL.....	12
1.2 Brentuximab Vedotin	13
1.3 Study Rationale	14
1.4 Rationale for New Cohort :.....	15
2 STUDY OBJECTIVES.....	17
2.1 Primary Objective.....	17
2.2 Secondary Objectives.....	17
2.3 Objectives of the New Cohort	17
3 INVESTIGATIONAL PLAN	17
4 SELECTION OF PATIENTS	18
4.1 Inclusion Criteria	18
4.2 Exclusion Criteria	19

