rate to CR, among patients who were in PR or SD after 2 cycles of treatment, was 0, a new cohort of ~20 patients is now proposed to evaluate the impact of treating non-CR patients with a higher brentuximab vedotin dose of 2.4 mg/kg) during cycles 3 and 4 – within dose levels shown to be safe in previous studies. In the phase I dose escalation study of brentuximab vedotin (SG035-0001) by Younes et al. 2010, 2 dose levels were explored; 12 patients each were treated at dose levels 1.8 mg/kg and 2.7 mg/kg, with brentuximab vedotin administered on an every-3rd-week schedule. Of the patients treated at 2.7 mg/kg, 3 of 12 (25%) had a dose limiting toxicity compared to 1 of 12 (8%) treated at 1.8 mg/kg. DLT were grade 3 hyperglycemia, grade 3 prostatitis, and grade 3 febrile neutropenia. Due to similar rates of overall response and lower toxicity, 1.8 mg/kg given every 3 weeks was the dose and schedule chosen to move forward in phase 2 studies of Hodgkin and systemic anaplastic large cell lymphoma. Furthermore, in a recent phase II study, COH IRB#12282, a dose of 2.4 mg/kg was administered safely to patients with non-lymphomatous cancers, so we have chosen this same dose level. Although the phase I study did not show differences in response between 1.8 mg/kg and 2.7 mg/kg, we hypothesize that there may be a dose response. There are some reports of dose response relationship anecdotally in the initial pivotal trial where patients were given up to 16 cycles of BV at 1.8 mg/kg. One or two patients developed progressive disease when dose was reduced to 1.2 m/kg for toxicities and went into partial remission again when dose was increased to 1.8 mg/kg.

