2.3 Objectives of the New Cohort

As part of a new cohort, 20 additional patients will be accrued. Patients treated as part of the new cohort who do not achieve CR at the end of cycle 2, will receive an escalated dose of 2.4 mg/kg of brentuximab vedotin during cycles 3 and 4. In addition to the original objectives of the Phase II study, patients treated at the higher dose will also be evaluated for the impact of the higher dose on response rate and toxicity after cycle 4.

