4.3 Eligibility for 2.4 mg/kg dosing in the new cohort

- In addition to the inclusion/exclusion criteria as outlined above, to be eligible for treatment with the higher 2.4 mg/kg dose of brentuximab vedotin in the new cohort of 20 additional patients, best response after 2 cycles of brentuximab

vedotin administered at the 1.8 mg/kg dose, must be PR or SD as determined by radiographic imaging.

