5.9 Selection and Timing of Doses for Each Subject

All patients will receive 1.8 mg/kg SGN-35 administered as a single outpatient IV infusion on Day 1 of each 21-day treatment cycle.

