In accordance with the primary study objectives, we will perform descriptive statistical analyses on these data after the study is complete. With adequate follow-up time, the endpoints of PFS, overall survival (OS) will be assessed by Kaplan-Meier survival analysis and 95% confidence intervals will be calculated using Greenwood's formula. PFS will be defined as the time from first treatment day (post AHCT) until objective or symptomatic relapse or death as a result of lymphoma or acute toxicity of treatment. OS will be defined as the time from first treatment day (post AHCT) until death. The cumulative incidence of relapse/progression and non-relapse mortality will be calculated as competing risks.

8.2 New Cohort to Test Increased Dosing for Patients Not Achieving CR after Two Cycles

Based on previously published brentuximab vedotin response/toxicity data and data from the phase II portion of this study (see protocol section 1.3), we now propose to accrue up to 20 additional patients in a new cohort that will enroll until we have 10 patients who do not attain CR after two cycles of therapy, and are treated at the increased dose of 2.4 mg/kg of brentuximab vedotin for cycles 3 and 4. The goal of this study is to evaluate the impact of treating non-CR patients (after two cycles of therapy) at an increased dose (from 1.8 mg/kg to 2.4 mg/kg) during cycles 3 and 4. We believe that the 2.4 mg/kg dose will be well tolerated (defined as $\leq 33\%$ of patients with \geq grade 3 non-hematologic toxicity that is assigned an attribution level of at least possibly related to the study drug during cycle 3 or 4) and that treating these patients at the increased dose will increase the CR rate.

With a CR rate of 33.3% -after two cycles of therapy, we expect to achieve 10 patients without CR (in the first 2 cycles) after 15 patients are enrolled (maximum enrollment 20, which has $>90\%$ chance of having 10 patients without CR in first two cycles). With 10 patients treated at the escalated dose of 2.4 mg/kg, with a conversion rate of 25%, the probability of not getting at least one response is less than 6%. If the first 2 cycle response data are pending, accrual will not hold. Accrual will only hold based on stopping due to toxicity, or when 10 patients are treated at the escalated dose of 2.4mg/kg. Patients who are treated with at least one cycle at 2.4 mg/kg will be evaluable at that dose level, even if later dose reduced or discontinued.

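### A new-cohort patient with progressive disease after cycle 2 has conflicting dose instructions, and the accrual figure in section 8.2 counts every patient without CR as a candidate for 2.4 mg/kg

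*Combined protocol and SAP*

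**What the plan says.** **Passages that escalate all patients without CR.** The Protocol Summary, under the new-cohort objectives, states "Those patients who do not achieve CR at the end of cycle 2 will receive a dose of 2.4 mg/kg". Its treatment paragraph states "Patients who do not achieve a CR (e.g., PR or SD) after 2 cycles of treatment, will be treated at a dose of 2.4 mg/kg"; there PR and SD are only examples. Section 2.3 repeats that patients "who do not achieve CR at the end of cycle 2, will receive an escalated dose of 2.4 mg/kg". Section 1.4 describes enrolling until ten non-CR patients have been treated at the higher dose. Section 8.2 enrolls "until we have 10 patients who do not attain CR after two cycles of therapy" and adds that these patients are treated at the increased dose.

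**Passage that restricts escalation.** Section 4.3 sets the eligibility rule for 2.4 mg/kg: best response after two cycles "must be PR or SD as determined by radiographic imaging".

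**Passage that does not mention escalation.** Section 5.9 states "All patients will receive 1.8 mg/kg SGN-35 administered as a single outpatient IV infusion on Day 1 of each 21-day treatment cycle", without an exception for the new cohort.

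**Context.** Section 7.1 classifies each assessment as PD, SD, PR or CR and bases the investigator's treatment decisions on it. Section 8.2 makes a patient evaluable at 2.4 mg/kg after at least one cycle at that dose. It calls the dose well tolerated if no more than 33% have related non-hematologic toxicity of grade 3 or higher in cycle 3 or 4. The experience that motivated the cohort, in section 1.4, is that the conversion rate to CR "among patients who were in PR or SD after 2 cycles of treatment, was 0".

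**The concern.** Take a new-cohort patient whose cycle 2 scan shows PD. The Summary and 2.3 direct this patient to 2.4 mg/kg, 4.3 makes the patient ineligible for it, and 5.9 gives 1.8 mg/kg. The Summary through section 12 contain no rule for treatment after PD. (The appendices listed in the contents were not in the text reviewed.) The study has two centers, and each could follow a different section and believe that it complied.

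The conflict carries into the analysis. Whether a PD patient is escalated determines whether that patient counts toward the 10 that end accrual, toward the conversion rate and toward the tolerability criterion. The comparison in 1.4 rests on PR or SD patients only, so a group of 10 that includes PD patients is no longer like for like. The accrual planning in 8.2 is also built on all patients without CR, which is wider than the group that 4.3 admits.

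**Working it through.** **1. Reproduce the figures in 8.2.** Inputs from 8.2: CR rate after two cycles 33.3%, so 2/3 are without CR; target 10; maximum 20; conversion rate 25%.

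- Expected enrollment: 10 / (2/3) = 15.0. Stated: 15.
- Chance of at least 10 without CR among 20: P(X ≥ 10), X ~ Binomial(20, 2/3) = 96.2%. Stated: above 90%.
- Chance of no conversion among 10: 0.75^10 = 5.6%. Stated: below 6%.

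All three reproduce. The first two apply to escalated patients only if every patient without CR is escalated.

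**2. Recompute accrual under the 4.3 rule.** If only PR or SD qualify, the eligible share is p = 2/3 − d, where d is the proportion of enrolled patients with PD at cycle 2. The documents do not give d, so it is assumed over a range.

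| Assumed PD rate d | Eligible share p | P(at least 10 of 20) | Expected enrollment 10/p, ignoring the cap |
|---|---|---|---|
| 0% | 0.667 | 96.2% | 15.0 |
| 3% | 0.637 | 93.1% | 15.7 |
| 5% | 0.617 | 90.2% | 16.2 |
| 10% | 0.567 | 79.7% | 17.6 |
| 15% | 0.517 | 64.6% | 19.4 |
| 20% | 0.467 | 46.8% | 21.4 |

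The chance falls below 90% once d exceeds about 5%.

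**3. How likely is the conflict to arise?** The chance of at least one PD patient among the 15 expected is 1 − (1 − d)^15: 53.7% at d = 5%, 79.4% at 10% and 91.3% at 15%.

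**4. If all patients without CR are escalated.** The accrual figures stand, but the 10 may include PD patients. Suppose that PD patients cannot convert (an assumption) and that the rate among PR or SD patients is 25%. With two PD patients among the 10, the expected rate over all 10 is 0.25 × 8/10 = 20%. The comparison with the zero in 1.4 is then diluted by patients of a kind not included there.

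**The case against.** The strongest reply is that the intent is clear. Section 4.3 is the dedicated eligibility rule for the higher dose, the Summary refers readers to the body for eligibility criteria, and wherever the non-CR categories are named they are PR and SD. Section 1.4 even moves from PR or SD to non-CR within one sentence, as if the second were shorthand for the first. This makes a PR/SD-only intent plausible. It does not remove the unqualified instructions in the Summary and 2.3, the non-CR count in 8.2 or the single dose in 5.9, and it leaves open what applies to a PD patient.

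A reader might also draw stronger conclusions that the documents do not support:

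- **That the figure below 6% is wrong.** It is not. Section 8.2 conditions on a 25% conversion rate among the 10 treated, and 0.75^10 = 5.6%. The values 0.75^9 = 7.5% and 0.75^8 = 10.0% apply only if one or two PD patients are assumed unable to convert, or are left out of the analysis. That is a different condition.
- **That the denominators are a separate gap.** Section 8.2 makes anyone with one cycle at 2.4 mg/kg evaluable, so the denominator is known once the dose is known. The uncertainty follows from the dosing conflict.
- **That four cycles are mandatory for everyone, PD included.** Section 1.3 speaks of a maximum of four, and 7.1 bases treatment decisions on the response assessments. Neither is a rule for PD, but together they do not compel continued treatment.
- **That the PD share can be read from 1.4.** With ORR 75% and CR 33.3%, (1 − 0.75)/(1 − 0.333) = 37.5% of patients without CR have SD or PD. That bounds the two together and says nothing about PD alone. Moreover, 75% of 30 evaluable patients is 22.5, so the ORR cannot be exact on that denominator.

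Finally, the cohort has no formal hypothesis test, so the effect is on planning and interpretation and not on an error rate.

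**Conclusion.** The conflict is in the current text and does not depend on any assumption: the Summary, 1.4, 2.3 and 8.2 speak of patients without CR, 4.3 admits only PR or SD, and 5.9 keeps everyone at 1.8 mg/kg. A PD patient at cycle 2 is foreseen but has no consistent instruction.

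The size of the statistical consequence does depend on the PD rate, which is assumed here. If 4.3 applies, the chance of reaching 10 within 20 is 90.2%, 79.7% or 64.6% at PD rates of 5%, 10% or 15%, against 96.2% as planned; at 0% nothing changes. If all patients without CR are escalated, the accrual figures hold, but the 10 may no longer match the PR or SD group in 1.4. The arithmetic in 8.2 is otherwise correct. The amendment should resolve this; the point does not call the cohort's design into question.

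**What to change.** 1. Reconcile the Summary (objectives and treatments), 1.4, 2.3, 4.3, 5.9 and 8.2, so that one definition states which cycle 2 response categories are escalated and what applies to a patient with PD. Which rule that should be is for the sponsor and the investigators; this review does not choose it.
2. Use that definition in 8.2 for the count of 10, the expected enrollment and the chance of reaching 10 within 20. If PD patients are not eligible, restate both accrual figures with the PD rate assumed.
3. Report conversion to CR among escalated patients who were PR or SD at cycle 2, to match the group in 1.4. State in 8.2 which cycle 2 categories enter the tolerability denominator.
4. Keep PD patients in the denominators of the new cohort's overall response and CR rates, whatever they receive after cycle 2.

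The cost is amendment wording in the sections listed and possibly a less favourable accrual figure. The wording itself adds no procedures and leaves the maximum of 20 unchanged.

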6.4.2 Disease Response Assessments

Responses will be assessed (between Days 15 and 21) as follows as defined in Section 7.1:

- Dedicated CT of chest, neck, abdomen, and pelvis or CT/PET: Cycles 2 and 4
- PET: Cycle 4

In addition, bone marrow aspirate and biopsy are required to confirm responses in patients who have bone marrow involvement at baseline (see Section 7.1). The follow-up bone marrow aspirate and biopsy must be done within 2 weeks of documentation of response. Once the bone marrow is negative no further bone marrow evaluations are required.

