7.1 Response Assessments

Treatment response will be assessed by dedicated spiral CT scan of chest, neck, abdomen, and pelvis and PET scans performed at protocol-specified time points (see Appendix Section 14.1 and Section 6). The determination of antitumor efficacy will be based on objective response assessments made according to the Revised Response Criteria for Malignant Lymphoma (Cheson et al. 2007) and treatment decisions by the investigator will be based on these assessments. Clinical response of progressive disease (PD), stable disease (SD), partial remission (PR), or complete remission (CR) will be determined at each assessment. Selection of up to 6 of the largest dominant nodes or nodal masses to follow for response assessment must be PET FDG-avid at baseline. Investigator evaluation of baseline radiographic assessment will enable study enrollment per Inclusion Criteria based on the presence of measurable disease > 1.5 cm evidenced by CT scan of the neck/chest/abd/pelvis or CT/PET scans. In addition, per the Revised Response Criteria for Malignant Lymphoma, these nodes or masses should be selected according to all of the following: they should be clearly measurable in at least 2 perpendicular dimensions; if possible they should be from disparate regions of the body; and they should include mediastinal and retroperitoneal areas of disease whenever these sites are involved.

If the bone marrow was positive at baseline, a follow-up bone marrow aspirate and biopsy is required and must be negative for assessment of a CR. If the follow-up

morphology is indeterminate, the biopsy tissue must be negative by immunohistochemistry or the patient will be assessed as a PR.

Tumor imaging will be performed at screening, cycle 2, and 4.

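### In marrow-positive new-cohort patients with a complete cycle-2 scan response, the sections conflict on CR status and cycle-3 dose, and a late negative marrow could be recorded as a conversion.

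*Combined protocol and SAP*

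**What the plan says.** Five places bear on cycle-2 status in a patient whose marrow was positive at baseline.

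- **Protocol Summary, efficacy data:** on the marrow biopsy, "If positive at baseline, it will be performed after 4 cycles of brentuximab vedotin". No earlier repeat is listed.
- **Section 6.4.2:** "Responses will be assessed (between Days 15 and 21) as follows", with imaging at cycles 2 and 4. It adds that "bone marrow aspirate and biopsy are required to confirm responses in patients who have bone marrow involvement at baseline", and on timing: "The follow-up bone marrow aspirate and biopsy must be done within 2 weeks of documentation of response".
- **Section 7.1:** a status of PD, SD, PR "or complete remission (CR) will be determined at each assessment". If the marrow was positive at baseline, "a follow-up bone marrow aspirate and biopsy is required and must be negative for assessment of a CR".
- **Section 2.3:** new-cohort patients "who do not achieve CR at the end of cycle 2, will receive an escalated dose of 2.4 mg/kg" in cycles 3 and 4. The Summary agrees, and keeps patients in CR at 1.8 mg/kg.
- **Section 4.3:** to be eligible for 2.4 mg/kg, best response after two cycles "must be PR or SD as determined by radiographic imaging". Marrow is not mentioned.

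Section 8.2 enrolls until 10 patients without CR after two cycles have been treated at 2.4 mg/kg, and looks at their conversion to CR. Section 8.1 describes response by CT and/or PET, again without marrow.

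**The concern.** Cycle-2 CR status does two jobs in the new cohort. It separates 1.8 mg/kg from 2.4 mg/kg, a dose above the MTD stated in Section 1.3. It also fixes the starting point of the conversion analysis, because only patients called non-CR and escalated enter the group of 10. If sections disagree about that status, two centers acting in good faith could give the same patient different doses and put that patient on different sides of the denominator.

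There is also a possible bias in one direction. A patient called non-CR at cycle 2 only because no marrow result was available, and called CR after cycle 4 once a negative marrow is in hand, looks like a conversion. The disease need not have changed after cycle 2. Section 1.4 gives the comparison as an observed conversion rate of 0 at 1.8 mg/kg, so a single such case is visible.

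**Working it through.** **1. The plan's own figures (Section 8.2).** These reproduce.

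- No conversion in 10 at a 25% rate: 0.75^10 = 0.0563, stated as under 6%.
- Expected enrollment for 10 non-CR patients at a CR rate of one third: 10 / (2/3) = 15, as stated.
- At least 10 non-CR among 20: binomial tail with p = 2/3 gives 0.962, stated as over 90%.

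**2. The sections side by side.** Take a new-cohort patient with positive baseline marrow and a complete response on the cycle-2 scan.

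| Rule followed | Cycle-2 position | Cycle-3 dose that follows |
|---|---|---|
| 7.1 for status, Summary for marrow timing | Not CR, no marrow yet | 2.4 mg/kg (Summary, 2.3) |
| 4.3 | Imaging is not PR or SD | Not eligible for 2.4 mg/kg |
| 7.1 with 6.4.2, marrow negative before dosing | CR | 1.8 mg/kg |
| 7.1 with 6.4.2, marrow positive before dosing | Not CR | 2.4 mg/kg by 2.3, but not eligible by 4.3 |
| 7.1 with 6.4.2, marrow after the dose is due | Not known at dosing | Not settled |

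If the scan shows PR or SD, every section agrees on non-CR. The conflict is confined to patients who are both marrow-positive at baseline and complete responders on the cycle-2 scan.

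**3. Timing under 6.4.2.** Scan on days 15–21, plus 14 days, gives a limit between day 29 and day 35. With 21-day cycles, cycle 3 is due on day 22. The limit is therefore 7 to 13 days after the dose is due.

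**4. Effect of one artefactual case.** With no true conversion among 10 escalated patients, the result is 0/10, exact 95% CI 0–30.8%. With one patient reclassified by a late negative marrow it is 1/10 = 10%, exact 95% CI 0.3–44.5%.

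**5. How often a patient could be exposed.** The documents do not give the marrow-positive share, g. I assume 5–15%, and a scan-CR rate of one third (the 33.3% in Section 8.2) that does not depend on marrow status. Then P(at least one among n) = 1 − (1 − g/3)^n, and the expected number is n × g/3.

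| g | n | Expected | P(at least one) |
|---|---|---|---|
| 5% | 15 | 0.25 | 22.3% |
| 5% | 20 | 0.33 | 28.5% |
| 15% | 15 | 0.75 | 53.7% |
| 15% | 20 | 1.00 | 64.2% |

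**The case against.** The strongest reply is that a false conversion needs a mixture of rules that no single body section sets out. Under 7.1 with 6.4.2, a documented cycle-2 response triggers a marrow within two weeks, so it is not left to cycle 4. Under 4.3, a complete responder on imaging is not eligible for 2.4 mg/kg and never joins the 10. The artefact arises if status comes from 7.1 and marrow timing from the Summary, which is an abbreviated list and does not say that the marrow is done only after cycle 4. It can also arise if the marrow under 6.4.2 comes after the dose. This stands as a limit on the bias claim, but it does not remove the conflict over status and dose. Nothing in 6.4.2 prevents a marrow before day 22, and nothing requires one. Waiting for a result is not provided for: the three-week delay in Section 5.5 is for recovery from toxicity, and Section 9.1 excuses up to three days for other causes.

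Section 7.1 also says that the investigator's treatment decisions rest on its response assessments. That points toward 7.1, but leaves the separate eligibility condition in 4.3 in place.

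The trial's own data show no sign of the artefact. Section 1.4 reports 30 evaluable patients and no change from PR to CR between cycles 2 and 4. The formula above with n = 30 would give a 40% (g = 5%) to 79% (g = 15%) chance of at least one exposed patient. This is mildly reassuring. It does not show absence, because the number of marrow-positive patients and the way their status was set are not reported.

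The study flow chart in Appendix 14.1, to which 7.1 refers for time points, was not in the text available to me and may state marrow timing.

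Three stronger readings are tempting and are not supported:

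- A reader might take 22–64% as the chance of a false conversion. It is only the chance of enrolling an exposed patient. A false conversion also needs 4.3 not to be applied, no marrow result before the dose, a scan response that is maintained, and a negative later marrow.
- A reader might infer that one case meets an efficacy criterion in 8.2. That section gives a probability of seeing at least one response, which supports the choice of 10 patients. It sets no success threshold.
- A reader might infer that 4.3 declares a complete scan responder with positive marrow to be in CR for dosing. It only limits who may receive 2.4 mg/kg.

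**Conclusion.** The conflict is real and follows from the text without any assumption. For a marrow-positive patient with a complete scan response at cycle 2, Section 7.1, the Summary, 6.4.2 and 4.3 do not yield one status or one cycle-3 dose. The membership of the conversion group in 8.2 changes accordingly.

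The bias is possible but conditional. If it occurs once, it adds 10 percentage points to a rate whose reference is 0, although the two exact intervals overlap widely. Few patients are likely to be exposed: the expected number is 0.25 to 1.0 under the assumed 5–15% marrow-positive share and an independent one-third scan-CR rate. I take no view on which clinical rule or dose is right.

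**What to change.** The sponsor should reconcile the Summary and Sections 2.3, 4.3, 6.4.2, 7.1 and 8.1–8.2 so that one stated determination of cycle-2 CR governs the cycle-3 dose in patients with positive baseline marrow, with marrow timing consistent with it. Which clinical rule applies is for the sponsor to decide.

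Whichever is chosen, Section 8.2 should:

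- apply the same CR definition at cycle 2 and cycle 4;
- count a conversion only where cycle-2 status was fully assessed under that definition;
- list separately any change in status that is due to marrow alone.

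The cost is protocol wording and one extra line in the analysis. No procedure is added.
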